1 PROTOCOL SUMMARY AND/OR SCHEMA

This phase I/II trial will assess the toxicity and pharmacokinetics (PK) of the humanized anti-GD2 x anti-CD3 bispecific antibody (hu3F8-BsAb) in phase I and the anti-tumor activity of hu3F8-BsAb in phase II. In phase I, dosages of hu3F8-BsAb follow a dose-finding design in order to determine the maximum tolerated dose (MTD) in cohorts of patients with relapsed/refractory neuroblastoma (NB), osteosarcoma, or other GD2(+) solid tumors. The recommended phase II dose (RP2D) will be established. Hu3F8-BsAb PK will be also evaluated. In phase II, patients with relapsed/refractory NB (Group 1) and osteosarcoma (Group 2) will be treated with hu3F8-BsAb at the RP2D and anti-tumor activity will be assessed.

2 OBJECTIVES AND SCIENTIFIC AIMS

2.1 Phase I

Primary Objective:

• To establish the safety of hu3F8-BsAb, and determine the maximum tolerated dose (MTD) and the recommended phase II dose (RP2D).

Secondary Objectives:

- To study the pharmacokinetics of hu3F8-BsAb.
- To evaluate human anti-human antibody (HAHA).
- Assess the anti-tumor activity and overall response rates of hu3F8-BsAb in patients with relapsed or refractory NB, osteosarcoma and other GD2(+) tumors.

Exploratory Objectives:

- To study immunological effects of hu3F8-BsAb
- To study the effects of hu3F8-BsAb on bone marrow (BM) RNA
- To study the effects of stool microbiome of the activity of hu3F8-BsAb.

2.2 Phase II

Primary Objectives:

• In Group 1: Assess the overall response rates of hu3F8-BsAb in patients with relapsed or refractory NB.

In Group 2: Assess the progression free survival (PFS) in patients with relapsed or refractory osteosarcoma at 4 months from the first hu3F8-BsAb treatment.

Secondary Objectives:

- To evaluate the duration of complete remission in groups 1 and 2.
- In Group 2: Assess the overall response rates of hu3F8-BsAb in patients with relapsed or refractory osteosarcoma.
- To continue to assess the safety/toxicity of hu3F8-BsAb.
- To evaluate HAHA.

Exploratory Objectives:

- To assess overall survival (OS) and PFS after treatment with hu3F8-BsAb.
- To study immunological effects of hu3F8-BsAb
- To study the effects of hu3F8-BsAb on BM DNA and RNA (Neuroblastoma patients only).
- To study the effects of stool microbiome of the activity of hu3F8-BsAb.

3 BACKGROUND AND RATIONALE

3.1 Disease background

NB is the most common extracranial solid tumor of childhood; approximately 700 children are diagnosed each year in the United States. 50-60% of patients present with an unresectable primary tumor and metastasis in BM.¹ Intensive chemotherapy with or without myeloablative therapy, surgery, radiation, and most recently, anti-GD2 immunotherapy have improved event free survival rates in patients with metastatic disease diagnosed >18months of age to approximately 40%.²⁻⁴ Somatic MYCN amplification is associated with a poorer prognosis. In addition, treatment for relapsed NB remains even more inadequate. A recent review of outcomes after relapse from the International Neuroblastoma Risk Group Project found that 5 year post-relapse overall survival for stage 4 NB was only 8%. Stage 4 patients with MYCN amplification did worse, with a 5-year post-relapse overall survival (PRS) of only 4%. Thus, a search for more effective therapies for stage 4 patients and relapsed patients is warranted.⁵⁻⁷

Osteosarcoma is a primary bone malignancy that occurs predominantly in children and adolescents with about 400 newly diagnoses each year in the United States. Patients with localized disease have 65-70 % long-term relapse free survival with systemic chemotherapy (combination methotrexate, doxorubicin, and cisplatin [MAP]) and aggressive surgical resection,⁸ whereas >80% of patients with detectable metastases at diagnosis have relapse after contemporary therapy.⁹ When osteosarcoma recurs, the outcome is dismal. Complete surgical remission is one of the important favorable prognostic factors in recurrent osteosarcoma; 5-year PRS of patients who had complete resection of recurrence was 39% whereas and 3-year PRS of those who did not have complete surgery was 0%.¹⁰⁻¹³ Multiple clinical trials of novel agents including ixabepilone, oxaliplatin, trasutuzumab, IGF-1R inhibitors, and mTOR inhibitors have been conducted but no improvement of survival was achieved.¹⁴⁻¹⁸ A recent

retrospective analysis of seven phase II trials conducted by Children's Oncology Group (COG) and its predecessor groups showed that PFS at 4 months from time of enrollment in patients with relapsed measurable disease was 12%.¹⁹

[figure not shown]
Currently, the limits of treatment intensity have been reached in up-front therapies in NB and osteosarcoma, leaving limited options for cytotoxic therapies upon relapse; antibody based immunotherapy is therefore particularly appealing in this heavily pre-treated population given its lack of significant acute hematologic toxicity and absence of long term side effects.

[figure not shown]
3.2 Rationale for anti-GD2 antibody

[figure not shown]
3.2.1 GD2 as an ideal target for antibody-based therapy in NB and other solid tumors

GD2 is an adhesion molecule abundant on NB and other solid tumors. Specifically, GD2 is expressed by 100% of NB,²⁰ 88% of osteosarcomas,²¹ >50% of melanomas,²² 70% of desmoplastic small round cell tumors (DSRCT)²³, and 93% of soft tissue sarcomas including liposarcoma, fibrosarcoma, malignant fibrous histiocytoma, leiomyosarcoma, and spindle cell sarcoma,²⁴ as well as brain tumors.²⁵ It is rarely expressed in normal tissues except neurons and skin cells. This antigen is genetically stable and relatively inert on the cell membrane. GD2 expression is rarely lost, even after relapse in patients previously treated with anti-GD2 therapy.^{26,27}

3.2.2 Experience with 3F8: anti-GD2 murine monoclonal antibody in high risk NB

[figure not shown]

3.3.2 Humanized 3F8 bispecific antibody

3.4 Pre-clinical studies of hu3F8-BsAb

3.4.1 In vitro cytotoxicity

[figure not shown]
3.4.3 Pre-clinical toxicology

[figure not shown]

Version: 18-034 A(10) Date 13-Jan-2022

3.4.4 **Pre-clinical pharmacokinetics (PK)**

3.5 Rationale for phase I study of hu3F8-BsAb

OVERVIEW OF STUDY DESIGN/INTERVENTION

4.1 Design

4.1.1 Phase I

Initially the phase I study will follow a dose-escalation escalation schema with 1 patient assigned per dose until the first \geq Grade 2 toxicity (except for Grade 2 sinus bradycardia, sinus tachycardia, urticaria, fever, nausea, vomiting, diarrhea, urticaria, headache, paresthesia, electrolyte disturbances, pain) is observed, then the subsequent dose allocation will follow the Continual Reassessment Method (CRM).^{75,76}a. Eligible patients will include relapsed or refractory NB, osteosarcoma, and GD2 (+) solid tumors. In each cycle, hu3F8-BsAb is given on Days 1 and 8. PK is assessed by blood draws. Patients are monitored for DLT until Day 28. Patients with DLT will come off treatment. HAHA titer will be measured after each cycle. Extent of disease evaluation will be performed after the second dose of cycle 2 and cycle 4, then every 3 months thereafter. A total of 4 cycles will be given. If patients experience no life-threatening toxicity clearly attributable to hu3F8-BsAb, do not develop progression of disease (PD) and continue to meet all eligibility criteria, they have the option of receiving additional cycles up to 2 years from the start of hu3F8-BsAb treatment. Patients may continue therapy beyond 4 cycles even if they achieve remission, see study design Figure 6.

The duration of each subsequent cycle is 28 days with hu3F8-BsAb being given on Days 1 and 8. MTD is defined as a maximum dose level at which ≤ 1 of 6 patients experiencing DLT. The RP2D will be decided based on the safety data in the phase I and can be MTD or lower. If MTD is not reached, RP2D may be determined on the basis of PK studies. If no DLT is observed, the RP2D will be determined as a minimum dose that gives the highest hu3F8-BsAb serum levels based on the PK data. For example, the RP2D of hu3F8 monoclonal antibody was decided as 9 mg/kg/cycle because the serum hu3F8 levels reached a plateau beyond 8.4 mg/kg/cycle with no DLT (see Section 3.2.3). After cycle 2, intra-patient dose escalation will be permitted i.e. patients can receive the highest dose that has been evaluated and proven safe by DLT assessment.

[figure not shown]

Figure 6 Study design

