9 TREATMENT/INTERVENTION PLAN

- 9.1 Phase I
- 9.1.1 General Outline

During phase I approximately 0.5 ml of the first Bs-Ab infusion will be collected about half-way through the infusion and assayed in Neuroblastoma research laboratory to determine quantity of hu3F8-BsAb in the final infusion product. In cycle 1, blood is drawn for PK studies as described in Section 9.1.4. Patients are admitted for dose 1 of cycle 1 of treatment and will be inpatient for approximately 4 days (minimum 48 hours) though the duration of stay may change if clinically indicated. Subsequent doses can be administered inpatient or outpatient. Patients are monitored for DLT clinically with physical examination, CBC and complete chemistry until Day 28. Patients with DLT will come off treatment HAHA titer is measured after each cycle. HAHA draws require about 5mL of serum. If HAHA develops, cycles are deferred for up to 4 months until HAHA titer until <1300 U/ml. Extent of disease evaluation will be performed after the second dose of hu3F8-BsAb in cycle 2 and cycle 4, every 3 months thereafter. (Table 6) A total of 4 cycles will be given.

Patients with no life-threatening toxicity clearly attributable to hu3F8-BsAb, no PD, and continuing to meet all eligibility criteria (with subsequently explained exceptions) have the option of receiving additional cycles up to 2 years from the start of the hu3F8-BsAb treatment. Inclusion criteria that no longer apply for patients to receive subsequent cycles are: disease status, since patients achieving remission may continue; and prior T cell immunotherapy timing restrictions, since all patients will have received Cycle 1 of hu3F8-BsAb. Even patients who achieve remission may continue therapy beyond

4 cycles. DLT and dose-schedule are described in Section 9.1.2 and 9.1.3. After cycle 2, intra-patient dose escalation will be permitted i.e. patients can receive the highest dose that has been evaluated and proven safe by DLT assessment. Patients will be admitted for at least 48 hours for their first escalated dose.

The treatment and evaluation schedule may require minor adjustment as clinically indicated or due to circumstance (e.g. due to PDH closure for holidays or due to inclement weather).

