9.3 HAHA testing

Blood (~5ml per draw) drawn before each cycle for HAHA testing will be measured using ELISA. Antiidiotype antibodies (Ab3, Ab3') will be also tested with the same blood samples.⁸¹

This blood sample may also be tested for HAMA. HAMA positivity is allowed and will not affect patients' eligibility for treatment.

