10.5 Urinalysis

- Phase I only: In cycle 1, urinalysis will be tested prior to each dose of hu3F8-BsAb and approximately one week after the second dose. (Pre-treatment urinalysis can be used for pre-cycle1 test.)
- **10.6** Liver and kidney function blood tests (ALT, AST, alkaline phosphatase, albumin, bilirubin, BUN and creatinine), and serum electrolytes (sodium, potassium, chloride, bicarbonate, magnesium, and phosphate).

- Phase I cycle 1: Before each dose of hu3F8-BsAb, within 72 hours after each dose of hu3F8-BsAb, and on approximately Day 15. (Pre-treatment test can be used for pre-cycle1 test.)
- For subsequent cycles in Phase I, and Phase II: Before each dose of hu3F8-BsAb. (Pre-treatment test can be used for pre-cycle1 test.)
- **10.7** Pregnancy test within 2 weeks before each cycle, if applicable.
- **10.8** Phase I only: Electrocardiogram will be done post the first infusion of hu3F8-BsAb on Day 1 and prior to the second dose hu3F8-BsAb on Day 8 during cycle 1. This must be done on the same day as the dose, but does not need to be immediately post or immediately prior.
- **10.9** Phase I only: Pharmacokinetic studies will be done as described in Section 9.1.4
- **10.10** Phase I and II: Cmax and Ctrough will be measured as described in Section 9.1.4
- **10.11** Ferritin and C-reactive protein
 - Phase I cycle 1: On Day 8 (prior to the second dose of hu3F8-BsAb) and approximately on Day 28.
 - For subsequent cycles in phase I, and phase II: If CRS is suspected based on clinical symptoms. (See Section 11.3)
- 10.12 LDH
 - Phase I cycle 1: On Day 8 (prior to the second dose of hu3F8-BsAb) and approximately on Day 28.
 - For subsequent cycles in phase I, and phase II: If CRS is suspected based on clinical symptoms. (See Section 11.3)
- **10.13** Blood will be obtained before each cycle of hu3F8-BsAb to assay for HAHA titers, then approximately every 3 months for 24 months from first hu3F8-BsAb dose, and then approximately every 6 months for up to 5 years from first hu3F8 dose or until patient is off study, whichever is earlier. This blood sample may also be tested for HAMA.
- **10.14** Blood will be tested for cytokine studies including IFN-y, IL-6, IL-8, IL-10.
 - Phase I cycle 1: cytokine studies should be tested prior to and ~ 6-8 hrs after the first and second infusion of hu3F8-BsAb, and on Days 2, 3, 4, 9, 10, and 11.
 - For subsequent cycles in Phase I and Phase II: If CRS is suspected based on clinical symptoms. (See Section 11.3)

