13 CRITERIA FOR REMOVAL FROM STUDY

- **13.1** Patients come off treatment if there is PD at any time. Best clinical judgment will be used to determine whether a patient must undergo tests between cycles to make sure disease is not progressing. Patients are followed for toxicities for 30 days from last treatment.
- 13.2 Patients come off treatment if they have DLT (during cycle 1 of phase I) or life-threatening toxicity clearly attributable to hu3F8-BsAb. Patients in the first stage of phase I (one patient per dose level cohort) who experience ≤ grade 2 toxicity, will not come off treatment but can continue at the same dose if they do not experience DLT and if toxicity subsides to <grade 2 within 35 days of dose 1 of Hu3F8-BsAb.

- **13.3** Patients who become pregnant during the study must be withdrawn from treatment
- **13.4** The investigators will make every reasonable effort to keep each patient in the study until all planned treatments and assessments have been performed. The investigators may discontinue study drug treatment for the following reasons:
 - Adverse events, including unacceptable toxicity or exacerbation of underlying disease, associated with study drug administration and necessitating discontinuation of treatment. Patients who are coming off treatment due to adverse events will be treated and followed according to established, acceptable medical practice. All pertinent information concerning the outcome of such treatment will be entered in the MSKCC institutional Clinical Research Database (CRBD). Patients will be followed until resolution or stabilization of the adverse event.

13.5 Off Study Criteria:

- Thirty days after the last dose of study drug for patients coming off treatment due to DP
- For patients coming off treatment due to adverse events, patients will be followed until the date the event returns to baseline or <Grade 3 (whichever is higher) or the date patients start another treatment, whichever is earlier.
- Death
- Lost to follow-up
- Withdrawal of consent. The patient's desire to withdraw from the study may occur at any time. The investigator should carefully consider whether the patient's withdrawal of consent is due to an adverse event, and if so, record the adverse event as the reason for withdrawal.
- Withdrawal by the physician for clinical reasons not related to study drug treatment in the absence of an adverse event.

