6.6.3.6. HAHA for Phases I and II

HAHA will be measured as previously described. The proportion of patients developing HAHA response (Positive / Negative) after hu3F8-BsAb therapy, as well as the continuous titer will be summarized at each timepoint for patients from the Safety Analysis Set.

In addition, HAHA data will be listed based on the Safety Analysis Set.

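### Protocol text and sampling tables disagree on HAHA timing, so on the tables most patients who stop for progression have no HAHA sample after their last cycle

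*Protocol*

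**What the plan says.** **After each cycle.** Protocol 4.1.1 states "HAHA titer will be measured after each cycle", and 4.1.2 and 9.2.1 say the same for Phase II. Protocol 9.1.1 repeats it for Phase I: "HAHA titer is measured after each cycle". SAP 2.1.1.1 and 2.1.2 carry this wording over.

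**Before each cycle.** Protocol 9.3 describes blood "drawn before each cycle for HAHA testing". Item 10.13 reads "Blood will be obtained before each cycle of hu3F8-BsAb to assay for HAHA titers, then approximately every 3 months for 24 months from first" dose, then about every 6 months to 5 years or until off study, whichever is earlier. Protocol Tables 6 and 7 and SAP Tables 2 and 3 give the same schedule. SAP 2.5.1.2 describes the pre-cycle draw. Protocol 9.1.4 also treats the HAHA blood as the pre-cycle sample, since it may be reused for the trough level.

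**Leaving the study.** Protocol 13.5 takes a patient off study "Thirty days after the last dose of study drug for patients coming off treatment due to DP" (read here as PD, progressive disease). Protocol 13.1 follows patients for toxicity over the same 30 days.

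**The endpoint.** Evaluating HAHA is a secondary objective in both phases. SAP 6.6.3.6 reports "The proportion of patients developing HAHA response (Positive / Negative) after hu3F8-BsAb therapy", by timepoint, in the Safety Analysis Set. SAP 7 lists departures from the protocol but does not settle the sampling time.

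**The concern.** While treatment continues, the sample before the next cycle is also the sample after the current one, so the wording does not matter. It matters for the last cycle. The design text calls for a sample then. The sampling sections and tables name none, and leave it to a 3-monthly follow-up draw that ends when the patient goes off study.

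If a site works from the tables, the missing sample falls mainly on patients who progress. How thoroughly HAHA is looked for would then depend on how long a patient stayed on treatment, which is itself an outcome. Once the patient is off study the sample cannot be recovered.

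**Working it through.** The documents give no target rate, precision or sample size for HAHA, so there is no figure of the plan's own to reproduce. The check is a calendar.

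**Inputs.** Doses on Days 1 and 8 of 28-day cycles (Protocol 4.1.1, 4.1.2). Off study 30 days after the last dose for progression (13.5). Follow-up draws about every 3 months, which 10.13 and Table 6 count from first dose. One month is taken as 30.4375 days, as in the SAP, so 3 months is 91.3 days.

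**Formulas for last cycle c.**
- Day 1 of the cycle, with its pre-cycle draw: 1 + 28(c − 1)
- Last dose: that day + 7
- Off study: last dose + 30
- Follow-up draws counted from first dose: 1 + 91 = Day 92, then 1 + 183 = Day 184
- Variant, with 3 months counted from the last pre-cycle draw: that day + 91

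| Last cycle | Pre-cycle draw | Last dose | Off study | Next draw, from first dose | Next draw, variant |
|---|---|---|---|---|---|
| 1 | Day 1 | Day 8 | Day 38 | Day 92 (missed) | Day 92 (missed) |
| 2 | Day 29 | Day 36 | Day 66 | Day 92 (missed) | Day 120 (missed) |
| 3 | Day 57 | Day 64 | Day 94 | Day 92 (inside by 2 days) | Day 148 (missed) |
| 4 | Day 85 | Day 92 | Day 122 | Day 184 (missed) | Day 176 (missed) |

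The first two scheduled disease evaluations follow the second doses of Cycles 2 and 4, so routine imaging tends to end treatment at two of the points where the draw is missed.

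**What each patient contributes on the tables.**
- Last cycle 1: no post-dose HAHA sample.
- Last cycle 2: one post-dose sample, before Cycle 2, which reflects Cycle 1 only. The patient can be counted negative although Cycle 2 was never tested.
- Last cycle 4: samples that reflect Cycles 1 to 3.

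**Denominator.** SAP 6.1 allows two rules. If a missing category is shown, the percentage is taken over the analysis population, so unsampled patients lower it. Otherwise it is taken over patients with data, and unsampled patients drop out. SAP 6.6.3.6 does not say which applies, and does not define an ever-positive patient.

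**Illustrations on assumed rates that are not in the documents.**
- Suppose a share s of patients leave with the last cycle untested, a share h of those first turn positive in it, and all are counted negative. The proportion is then low by s × h. With s = 0.20 and h = 0.05 that is 0.01. With s = 0.88 and h = 0.20 it is 0.176. The range is about 1 to 18 percentage points.
- For one patient treated for two cycles with a constant risk q per cycle, the true risk is 1 − (1 − q)² and the observable risk is q. For q = 0.10 that is 0.19 against 0.10, and for q = 0.30 it is 0.51 against 0.30.

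**The case against.** A reader might infer that HAHA is drawn only before cycles, that nobody who stops is ever tested for the last cycle, and that incidence is therefore understated. The documents do not support that.

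- Item 10.13 and the follow-up columns schedule draws for up to 5 years. Patients who stop without progression and stay on study are tested, and a Cycle 3 progressor may be. This stands, and it limits the point mainly to progressors. Other exits in 13.5, such as death, withdrawal, or another treatment after an adverse event, can also cut follow-up short.
- Nothing gives the tables precedence over the design text. A site that follows the design text would take the sample. This also stands: the finding is a conflict that can lose data, not a demonstrated loss.
- Downward bias is not shown for patients with no post-dose sample, because SAP 6.1 may remove them from the denominator. This stands for them. It does not answer the Cycle 2 stopper, who has a sample and can be counted negative. For that patient a positive result can be missed but not gained.
- It is tempting to size the problem from 4-month PFS in osteosarcoma: 18 × 0.88 = 15.8 failures at the 12% benchmark, or 18 × 0.60 = 10.8 at the 40% target. Those are failures by 4 months, which is later than four nominal cycles. They do not count patients who stop after Cycle 1 or 2. With the first scheduled imaging in Cycle 2, stopping after Cycle 1 for progression should not be assumed typical.
- HAHA incidence is descriptive, with no hypothesis or success rule. The Phase I association analyses in SAP 6.6.3.6.1 use HAHA only up to the last pre-dose sample before Cycle 4, so a missing post-Cycle-4 sample does not touch them. This stands. However, early stoppers still have fewer chances to test positive, and under SAP 5.2.1 missing response counts as non-response.

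**Conclusion.** The conflict is real and SAP 7 does not resolve it. If the sampling tables are followed, most patients who stop for progression have no HAHA sample after their last cycle: Cycles 1, 2 and 4 on the calendar from first dose, and Cycle 3 as well on the variant. Detection of HAHA then depends on time on treatment.

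The size of the effect cannot be derived from the documents, and the 1 to 18 point range is only as good as its assumed inputs. Understatement is clear only for patients counted negative on a sample that predates their last cycle. For patients with no post-dose sample the direction depends on a denominator that the SAP leaves open.

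The calendar assumes no cycle delays. A delay can change coverage: if Cycle 2 starts 56 days after Cycle 1, on Day 57, off-study falls on Day 94 and the Day 92 draw is just inside.

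Severity is minor to moderate. This is a descriptive secondary endpoint, and neither the primary endpoints nor the MTD is shown to be affected.

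**What to change.** 1. **Sampling.** Reconcile Protocol 9.3, 10.13 and Tables 6 and 7, and SAP Tables 2 and 3 and 2.5.1.2, with the design text. Take a HAHA sample before Cycle 1 and one after every cycle including the last. State that the post-cycle sample is the next pre-cycle draw or, if no further cycle is given, a draw within the 30-day follow-up of 13.1 and before off-study. Keep the 3-monthly draws for patients who stay on study.
2. **Analysis.** In SAP 6.6.3.6, report the ever-positive proportion among patients with at least one post-dose sample, and show the number without one. Because 6.6.3.6.1 is defined by pre-dose assessments, say there whether the final sample of a patient who stops before Cycle 4 counts.

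The cost is wording in both documents and at most one extra draw of about 5 mL per patient, which the design text already calls for and which fits the existing follow-up period. No efficacy or dose-finding analysis changes.
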